After informed consent is obtained, blood pressure will be obtained to confirm eligibility. Those with BP less than 120 mmHg systolic and 80 mm Hg diastolic, or greater than 140 mmHg systolic or 90 mmHg diastolic, will be considered as screening failures, and will not move on to the remaining enrollment visit activities. For those confirmed to have an eligible baseline blood pressure reading, a brief medical history will be obtained, randomization will be completed, and baseline study measures obtained, prior to the start of the intervention. Those scheduled for an enrollment visit will also be provided a copy of Appendix B, Handout to Study Participants, and/or a welcome email with details.

Inclusion Criteria:

Men and women, ≥ 18 years of age, with pre-hypertension, who have systolic BP ranging from 120-139 mm/Hg, or who have diastolic BP ranging from 80-89 mm/Hg.

Exclusion Criteria:

Blood pressure values that are outside of the range for prehypertension at the enrollment visit

Unable, unwilling, or incompetent to provide informed consent

Physically unable to come to the study visits, or to sit comfortably in a chair for up to two hours at a time

Prior diagnosis of hypertension

Ongoing need for medical treatment for hypertension, or for the use of medications commonly used for treatment of hypertension
Known cardiovascular disease
Known seizure disorder
Known or anticipated pregnancy (females of childbearing age will be tested for pregnancy prior to randomization)
Severe hearing impairment (because the subject will be using headphones during the interventions)
Ongoing need for treatment with opiate, benzodiazepine, or anti-psychotic medications, anti-depressant medications such as SSRI, SNRI, or tricyclic, and sleep medications such as zolpidem or eszopiclone
Anticipated and ongoing use of recreational drugs, alcohol, or energy drinks
Ongoing need for treatment with thyroid medications

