Participants are encouraged to discuss their participation with their health care provider following completion of the study because HIRREM may alleviate some of the need for medications they were on previously. Participants are requested to abstain from using any alcohol or recreational drugs during the intervention, and for at least six weeks following sessions since use of these substances may cause reversal or cessation of the benefits of HIRREM. In addition, the participants are also advised to suspend chiropractic, cranial-sacral therapy, and bio-energy work during the intervention, and for at least six weeks following.

Number of Subjects:

As a pilot study, involving an active control condition for which we as yet have no information regarding effect size, we are not able to calculate a sample size. In order to evaluate feasibility and effect size, and allowing for up to 20% drop outs, we will arbitrarily enroll up to 24 subjects to achieve a goal of having 20 subjects complete the study per protocol (estimated 10 per group).

Number of HCC/NCC Sessions and Length of Study:

All baseline measures, along with a brainwave assessment, will be obtained during an enrollment visit (V1). The intervention will commence 1-14 days later. Participants will receive 8-16 intervention sessions over a maximum of 4 weeks. HCC or NCC sessions will be about 1.5-2 hours in length. Participants may receive two intervention sessions during a half day period. All will receive a total of 6 sessions during the first three days of the intervention period. Participants will be encouraged to complete the remainder of the intervention sessions within two-three weeks, with a maximum of four weeks to complete the sessions. If done as two sessions per half day, subject involvement will thus require 4-8 half days during the intervention period. Following the initial 6 sessions, some sessions may be arranged as singles (one per day), if needed due to schedule issues.

One to seven days after the final intervention session there will be a post-intervention data collection visit (V2). All measures will be repeated, but no brainwave assessment will be obtained. Four to six weeks after completion of the intervention, there will be a post-intervention data collection visit (V3),

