with all measures repeated. Data collected at the V3 visit will comprise the primary outcome data for the study. A final data collection visit (V4) will occur 12-14 weeks after completion of the intervention, with repeat of the outcome measures, but no brainwave assessment. At V4, official study involvement is complete for those in the HCC group, while those randomized to the NCC group will be offered an opportunity to be scheduled to receive a course of HCC. Those who opt to do so will receive a course of acoustic stimulation linked to brainwaves, as described for the HCC group, and will continue to be followed for data collections at 1-7 days (V5), 4-6 weeks (V6), and 12-14 weeks (V7), as done during the initial intervention period, after completing their crossover HCC sessions.

Enrollment Visit:

Informed consent is obtained, and blood pressure is then obtained. Since all participants will have been documented to have prior blood pressure values that meet the parameters for prehypertension, and in light of variability associated with visits to the doctor, or other factors, if blood pressure values are too high, or too low on the initial measurements the potential participant will be allowed to rest for at least 3 minutes, and the blood pressure will be repeated. Those who still have blood pressure values less than 120 mmHg systolic pressure, and diastolic pressure less than 80 mmHg, and thus do not meet criteria for pre-hypertension, will be considered as screen failures. Those with blood pressure that is still higher than 140 mmHg systolic or 90 mmHg diastolic, will be also be considered as screen failures. They will not be assigned a study number, and will be excluded from further participation. Those with blood pressure values that are too high will also be advised to follow up with their medical provider. For those who meet blood pressure goals, notification of group assignment is made, and all baseline measures are collected, including a brainwave assessment. If not already completed via a REDCap link, a brief medical history form will be completed (Appendix C). The V1 visit will require about 2 hours of time.

Intervention Period:

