This is the first step in the HIRREM process. It occurs during the V1 enrollment visit, and will be performed on both groups. The assessment creates a map of frequencies and amplitudes, and informs the choice of protocols for the initial HIRREM sessions. Our pilot data also suggest that this information is also useful for correlating with autonomic function (HRV and BRS), and that changes can be observed in frequencies and amplitudes from pre- to post-HIRREM. For the assessment, with the participant in a sitting position, sensors are sequentially placed over six areas of the scalp to record one minute epochs of data while the brain is at rest, or on task, with eyes open and with eyes closed. For the assessment, measurements are taken at homologous regions of the bilateral hemispheres according to the 10-20 International System at F3/F4, C3/C4, P3/P4, T3/T4, FZ/OZ, and O1/O2 with both eyes closed (EC; one minute), and eyes open (EO; one minute) conditions ("Report of the committee on methods of clinical examination in electroencephalography: 1957," 1958). For EO assessments, subjects are given standardized tasks involving numerical digit recall (F3/F4), reading silently (C3/C4), math calculations (P3/P4), listening comprehension (T3/T4), and to relax with eyes open (O1/O2). A sixth midline measurement is taken at FZ/OZ, with an EO task to count number of appearances of a specific word as they read a standardized printed passage, with additional recordings at a seventh (FP1/FP2, given standardized tasks involving numerical digit recall), and eighth (CB1/CB2, relax with eyes open) location. The reference sensors are connected at A1/A2 and linked for assessments. The data are processed to identify patterns and imbalances of frequencies and amplitudes, which are used to generate specific protocols for the initial HIRREM session. The assessment takes about 30-45 minutes to complete. An assessment will be repeated at the V3 visit to allow comparison between brain patterns at baseline, and post-intervention, between the two groups.

HIRREM/Ambient Sound Sessions:

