The HIRREM process is individualized for each recipient, such that the specific protocols chosen, the session length, and the total number of sessions are variable. Technologists time sessions and chose protocols to facilitate an overall trend toward greater hemispheric symmetry and more optimal proportionation in frequency ranges, between and within cortical regions, based upon data from the initial assessment and the ensuing sessions (Gerdes et al., 2013). Each participant in the HCC group will receive at least 10 sessions. The final number of HIRREM sessions, which may be extended to as many as 16, will depend on continuous review of brain patterns relative to progress towards improved balance and quieting of electrical amplitudes, as well as progress and stability of self-reported status regarding symptoms such as sleep and stress.

Ambient nature sounds (NCC) were chosen as an active control because this approach may also facilitate recovery from stress-related sympathetic hyperarousal (Alvarsson, Wiens, & Nilsson, 2010). Exposure to nature sounds has been shown to facilitate reduced sympathetic activation in response to psychological stress (Annerstedt et al., 2013), which is relevant for those with hypertension, and also provides a credible control regarding the effects of expectation associated with a technological intervention, while also matching exposure to location, environment, exposure time, and staff contact for each study group.

Participants assigned to the NCC group will receive sessions in the same rooms, but will select from a variety of ambient sounds. Sessions will consist of 60-90 minutes of listening time, while in a zero gravity chair, and are intended to mirror the time, environment, eye state, and staff interaction

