Reaction testing will be evaluated by a drop-stick, clinical reaction time apparatus. It is constructed from a meter stick covered in friction tape with gradations. The modified meter stick is fixed to a weighted rubber cylinder. The apparatus is placed between the thumb and index finger of the subject and released at a random time during a countdown. The subject catches the apparatus and the distance fallen (cm) is converted to reaction. Following two practice trials, subjects perform eight trials, and a mean distance value is used for analysis. This is repeated with a second set of 8 trials later during the enrollment visit, and the mean distance value from the second trial will be used as the baseline value. Use of the average distance from the second set of trials will be used as the baseline value so as to avoid the impact of learning effect for this test. This simple clinical measure has been evaluated by Eckner et al, and demonstrated utility in testing comparable to computerized testing methods (Eckner, Kutcher, & Richardson, 2010). Our pilot data demonstrate improved reaction testing associated with use of HIRREM for athletes with persisting post-concussion symptoms (C. H. Tegeler et al., 2016).

Grip Strength:

Grip strength will be evaluated using a hydraulic hand dynamometer (Baseline Hydraulic Hand Dynamometer). The greatest force generated during three trials will be used for analysis (Roberts et al., 2011).

Statistical Analysis:

Continuous variables will be summarized with standard descriptive statistics, such as quartiles, means, and standard deviations, while categorical variables will be summarized with percentages and frequencies. LMMs will be employed to contrast longitudinal changes in systolic and diastolic blood pressure between the HCC and NCC groups. Mean contrasts will be used to compare the changes in blood pressure between groups from V1 to V3, our primary test of efficacy. Comparisons of changes in all secondary outcomes will be assessed in a similar fashion. Assumption and computation diagnostics will be assessed for all model fits (Cheng, Edwards, Maldonado-Molina, Komro, & Muller, 2010), and model adjustments and outcome variable transformations will be made as necessary. Data will be analyzed using SAS v9.4 (SAS Institute, Inc., Cary, NC) or the R Statistical Computing Environment.

Participant Compensation:

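### As written, V1 places randomization and notification of group before the other baseline measures, so baselines of self-reported and effort-dependent secondary outcomes could shift differently by arm

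*Combined protocol and SAP*

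**What the plan says.** Two places in the protocol describe the sequence at V1.

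- **Participants/Subjects.** Blood pressure comes first: "After informed consent is obtained, blood pressure will be obtained to confirm eligibility". For those who qualify, "a brief medical history will be obtained, randomization will be completed, and baseline study measures obtained, prior to the start of the intervention".
- **Enrollment Visit.** "For those who meet blood pressure goals, notification of group assignment is made, and all baseline measures are collected, including a brainwave assessment". The section does not say whether the participant, the tester or both are notified.

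Four other sections bear on the point.

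- **Reaction Testing.** The drop-stick baseline comes from the later of two sets: "This is repeated with a second set of 8 trials later during the enrollment visit, and the mean distance value from the second trial" is the value used.
- **Statistical Analysis.** After describing the V1-to-V3 contrast for blood pressure, the plan adds: "Comparisons of changes in all secondary outcomes will be assessed in a similar fashion".
- **HIRREM/Ambient Sound Sessions.** Nature sounds were chosen partly because this "provides a credible control regarding the effects of expectation associated with a technological intervention".
- **Brainwave Assessment**, and **Number of HCC/NCC Sessions and Length of Study.** Of the assessment: "It occurs during the V1 enrollment visit, and will be performed on both groups". Of the sessions: "The intervention will commence 1-14 days later".

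**The concern.** A baseline protects a comparison of changes because it is measured before anyone knows the arm, so the groups can differ on it only by chance. If participants learn their arm first, that knowledge may colour their answers on sleep, mood, anxiety and stress, or the effort they put into a maximal test. If only the tester knows, encouragement and scoring on the grip and drop-stick tests are still exposed.

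Any resulting difference at V1 carries into the V1-to-V2, V1-to-V3 and V1-to-V4 contrasts. The plan itself treats expectation as something to control and predicts larger gains with HIRREM, so disclosure before baseline works against its own safeguard. The pilot is also meant to supply effect sizes for larger trials, and a distorted baseline would be carried into them.

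**Working it through.** **1. Order of events.** The two descriptions of V1, side by side:

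| Step | Participants/Subjects | Enrollment Visit |
|---|---|---|
| Consent, then qualifying BP | first | first |
| Medical history | before randomization | mentioned last, unless already done online |
| Allocation | randomization | notification of group |
| Other baseline measures | listed after randomization | listed after notification |

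They differ on the medical history but agree that allocation precedes the other baseline measures. No section gives the reverse order, and none describes masking of participants or outcome testers.

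**2. Which baselines are exposed.**
- *Primary seated BP:* appears unaffected. The Blood Pressure section uses one method and one reading per visit for both eligibility and the primary outcome, and that reading precedes assignment.
- *Most exposed:* self-report scales, and the grip and drop-stick tests. Taking the second drop-stick set as baseline handles learning, but it is the later value in the visit.
- *Less exposed:* PSQI (one-month window), ESS (usual dozing), software-derived HRV and BRS, and the brainwave assessment.

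**3. How a shift enters the estimate.** Let d1 and d3 be the between-arm shifts caused by arm knowledge at V1 and V3. The difference in V1-to-V3 change is then off by d3 − d1. Reordering V1 sets d1 to zero and leaves d3.

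**4. Could a shift be seen afterwards?** The 95% half-width of a chance baseline difference is t(0.975, 2n−2) × SD × √(2/n). The SDs are the Table 2 baseline values, from 10 open-label participants with BP above 130/90. Applying them to pre-hypertension is an assumption, made only to set the scale.

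| Scale | SD | n = 10 per arm (t = 2.101) | n = 12 per arm (t = 2.074) |
|---|---|---|---|
| ISI | 7.2 | 2.101 × 7.2 × √0.2 = 6.8 | 6.1 |
| GAD-7 | 3.8 | 3.6 | 3.2 |
| CES-D | 11.7 | 11.0 | 9.9 |

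A shift smaller than these would look like ordinary imbalance.

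**5. What an assumed shift would do.** Suppose there is no true effect, d3 = 0, a two-sided 5% test and 10 per arm. With the Table 2 SD of ISI change (4.6), the standard error of the contrast is 4.6 × √0.2 = 2.06. Baseline shifts of 1, 2 and 3 points then give noncentralities of 0.49, 0.97 and 1.46. The false-positive rates are about 7.5%, 15% and 28%.

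Adjusting for baseline (ANCOVA) shrinks the bias to ρ × d1, where ρ is the V1–V3 correlation, but does not remove it. For a 0.5 SD shift with ρ = 0.5, the false-positive rate falls from 18.5% to 9.4%. With ρ = 0.7 it falls from 27.7% to 18.0%. The shifts and correlations are assumptions; the documents give neither.

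**The case against.** The strongest reply is that the text shows an unspecified order rather than a confirmed fault. Both sentences join the steps with a plain conjunction, the two sections place the medical history differently, and the recipient of the notification is not named. This stands as a limit on certainty. It does not remove the point, because both descriptions agree on allocation first and a site following either could collect baselines with the arm known.

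Second, nothing in the documents shows that d1 is material. The half-widths describe chance imbalance in any trial of this size, and the false-positive rates rest on assumed shifts. That is correct: these figures show that a shift would be hard to recognise and could matter, not that one will occur.

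Third, because the error is d3 − d1, shifts in the same direction partly cancel, and removing d1 alone could leave a larger net error. The algebra stands, and arm knowledge at follow-up may well be the greater exposure, since nature-sound participants choose their own sounds over 8 to 16 sessions. But relying on two unknown biases to cancel is no safeguard. A baseline taken before allocation leaves one source of error, at follow-up, to be dealt with separately.

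Fourth, the primary outcome is unaffected and this is a pilot of up to 24. That limits the severity. Since the pilot's purpose includes estimating effect sizes, it does not make the order unimportant.

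**Conclusion.** The concern holds. As written, the plan allows every V1 baseline except the qualifying seated blood pressure to be collected after the arm is assigned and disclosed. The risk falls mainly on self-reported and effort- or tester-dependent secondary outcomes.

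The size and direction of any shift cannot be derived from the documents. Under the Table 2 SDs, a shift below roughly 7 ISI, 4 GAD-7 or 11 CES-D points at 10 per arm could not be told from chance imbalance, so protection has to come from the order of V1 rather than from later analysis. Confidence is moderate, because the sentences may not be strict chronology and the person notified is not stated. It should be fixed, but it does not undermine the primary comparison.

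**What to change.** State one explicit V1 order, identical in Participants/Subjects and Enrollment Visit:

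1. consent;
2. qualifying blood pressure;
3. medical history and, where applicable, the pregnancy test (already required before randomization under Exclusion Criteria);
4. all baseline measures: questionnaires, autonomic recording, grip, both drop-stick sets and the brainwave assessment;
5. only then randomization, followed by notification of participant and staff.

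State who is notified and at what point. If practice already follows this order, a clarifying sentence in each section is enough.

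The cost is essentially nil. Both arms have the same measures, including the brainwave assessment, and sessions start at least a day later, so nothing at V1 depends on knowing the arm. Visit length and sample size do not change. Expectation effects at V2 to V4 are not resolved by this change and need their own treatment.

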The primary objective of this pilot study is to evaluate whether the addition of acoustic stimulation linked to brain activity (HIRREM, HCC), as compared to the addition of acoustic stimulation not linked to brain activity (ambient nature sounds, NCC), to continued current care for both groups, will reduce systolic and diastolic blood pressure in patients with documented blood pressure values that place them in the category of pre-hypertension.

Secondary Objectives:

[figure not shown]
Evaluate whether the addition of acoustic stimulation linked to brain activity (HCC group), as compared to the addition of acoustic stimulation not linked to brain activity (NCC group), to continued current care, will result in greater differential changes in a variety of physiological, behavioral, and function outcome measures outlined below.

1. Autonomic nervous system functions, as manifested by heart rate, HRV, and BRS. We expect to see greater changes in autonomic activity and an improvement of sympatho-vagal balance in the HCC group. This would be reflected as changes in heart rate, and an increase of HRV and BRS parameters such as the standard deviation of the R-R interval (SDRR), rMSSD, HF alpha, and Sequence Up, Down, or All.
2. Behavioral outcomes such as insomnia (assessed by the Insomnia Severity Index, ISI; Pittsburgh Sleep Quality Index, PSQI; and the Epworth Sleepiness Score, ESS), depression (as assessed by the Center for Epidemiological Studies-Depression Scale, CES-D), anxiety (as evaluated by the GAD-7), traumatic stress (as assessed by the PCL-C), and stress (as assessed by the Perceived Stress Scale, PSS). We expect to see greater improvement in these symptom inventory scores in the HCC group.
3. Overall quality of life as evaluated using the EQ-5D measure. We hope to see greater improvement in overall quality of life scores in the HCC group.
4. Functional performance evaluated using drop stick reaction testing. We expect to see more improvement in the HCC group.
5. Functional performance evaluated by grip strength, using a hand dynamometer. We expect to see greater improvement of grip strength in the HCC group.
6. Impact on comorbidities, for example a history of TBI/concussion, PTSD, ADHD, hot flashes, migraine, or insomnia. We expect to see more reduction of symptoms in the HCC group.

[figure not shown]
Overview:

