Continuous BP and HR are acquired from noninvasive finger arterial pressure measurements and ECG for a minimum of 10 minutes in subjects lying down quietly, supine. Systolic BP and beat to beat, RR, intervals (RRI) files generated via the data acquisition system (BIOPAC acquisition system and software, Santa Barbara, CA) at 1000 Hz are analyzed using Nevrokard SA-BRS software (by Nevrokard Kiauta, d.o.o., Izola, Slovenia) for measures of BRS, HRV and BPV as follows: Frequency Method. Power spectral densities of SBP and RRI oscillations are computed by 512 points Fast Fourier Transform (FFT) and integrated over specified frequency ranges (LF: 0.04-0.15 Hz; HF: 0.15-0.4 Hz). A Hanning window is applied and the squared-coherence modulus is computed if coherence is >0.5 as reported. The square-root of the ratio of RRI's and SBP powers is computed to calculate LF, HF alpha indices, which reflect BRS (16). Power of RRI spectra in LF, HF range (LFRR and HFRR) are calculated in normalized units and the ratio of LFRR/HFRR is used as a measure of sympathovagal balance. Power of SBP spectra calculated as LFSAP is used as a measure of BPV. Sequence Method. BRS calculated by this method is based on quantification of sequences of at least three beats (n) in which SBP consecutively increases (UP sequence) or decreases (DOWN sequence), which are accompanied by changes in the same direction of the RRI of subsequent beats (n+1). The software scans the RRI and SBP records, identifies sequences, and calculates linear correlation between RRI and SBP for each sequence. If the correlation coefficient exceeds a pre-set critical value (0.85), the regression coefficient (slope) is calculated and accepted. The mean of all individual regression coefficients (slopes), a measure of sequence BRS, is then calculated for Sequence UP, DOWN and TOTAL. Time-Domain Analysis. Three time-domain parameters are used for hemodynamic variability. HRV is determined by computing the standard deviation of normal to normal intervals (SDNN), and the root mean square of successive beat-to-beat differences in R-R interval duration (rMSSD). BPV is the standard deviation of the mean arterial pressure (SDMAP).

HRV and BRS Data Processing and Interpretation:

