Heart rate is measured as beat-to-beat intervals (RRI) recorded by pulse-wave recording, and will be analyzed using custom software developed by Matlab. Data can be loaded and viewed, and a subset of the data can be selected to avoid artifacts during device placement or removal. Outlier identification is performed by determining all IBIs which demonstrate a 30% difference from the mean of the previous four samples. Such outliers are removed from the data set. HRV statistics that are generated include mean, variance, SDNN, rMSSD, VLF, LF, HF, TP, LF/HF, sample asymmetry, sample entropy, and coherence ("Heart rate variability: standards of measurement, physiological interpretation and clinical use. Task Force of the European Society of Cardiology and the North American Society of Pacing and Electrophysiology," 1996). All of the algorithms for computation of these parameters are derived from information or source code from the Physionet archive. Data are saved to Excel spreadsheets for further statistical analysis by study team members.

Blood Pressure (BP):

For evaluation of blood pressure (BP) values that will be used to qualify for participation in the study, and for analysis of the primary outcomes, BP measurements will be obtained using an automated oscillometric blood pressure device. BP will be obtained in the left arm, with the participant sitting

comfortably, and the left arm resting on a desk/table. Three samples will be obtained and the last two averaged to get the value that will be used as the reading for that visit (Kaplan NM, 2010).

Insomnia:

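### The 30% interval rule leaves beats less than about 30% early in the HRV series, so SDNN and rMSSD are not computed on normal-to-normal intervals; the expected cost is noise in secondary outcomes

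*Combined protocol and SAP*

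**What the plan says.** The section HRV and BRS Data Processing and Interpretation describes one pipeline: "Heart rate is measured as beat-to-beat intervals (RRI) recorded by pulse-wave recording, and will be analyzed using custom software developed by Matlab". Its cleaning rule is "Outlier identification is performed by determining all IBIs which demonstrate a 30% difference from the mean of the previous four samples", followed by "Such outliers are removed from the data set". The only other cleaning step is that "a subset of the data can be selected to avoid artifacts during device placement or removal". The section gives no way to recognise ectopic beats, no interpolation, and no rule for differences that span a removed interval. It does not say whether the four reference samples include intervals already flagged.

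The section on autonomic cardiovascular regulation describes a second pipeline. Files from finger pressure and ECG, sampled at 1000 Hz, "are analyzed using Nevrokard SA-BRS software". Its time-domain measures are the "standard deviation of normal to normal intervals (SDNN), and the root mean square of successive beat-to-beat differences in R-R interval duration (rMSSD"). No outlier rule is given there. The protocol does not say which pipeline supplies the HRV values for analysis.

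Secondary Objectives, item 1, predicts for the HIRREM arm "an increase of HRV and BRS parameters such as the standard deviation of the R-R interval (SDRR), rMSSD", among others, and reads this as better autonomic balance.

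**The concern.** SDNN is meant to describe variation among normal beats, and rMSSD the differences between successive beats. An early beat that stays in the series adds large squared differences that have nothing to do with vagal tone, and it always raises that record's rMSSD. That is the direction the protocol reads as improvement. Records are short (a minimum of 10 minutes) and arms are small (about 10 completers each), so a few such beats in one person's record are not averaged away. The study also intends to provide effect-size estimates for larger trials, so avoidable noise in these measures has a cost beyond this pilot.

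**Working it through.** **Pilot figure.** Table 3 (18 service members): rMSSD 32.76 to 45.98 ms. 45.98 − 32.76 = 13.22, as printed. t = 13.22/3.00 = 4.41 on 17 df, two-sided p = 0.0004, consistent with the printed p < 0.001.

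**What the rule keeps.** Take a steady rhythm and a beat early by a fraction e.
- The early interval is flagged only if e ≥ 0.30.
- With a full compensatory pause, the next interval is 1 + e times normal and the trailing mean of the previous four is 1 − e/4. The pause is flagged if 1 + e ≥ 1.3(1 − e/4), that is e ≥ 0.3/1.325 = 22.6%.
- So below 22.6% both intervals stay. From 22.6% to 30% the early interval stays and its pause goes. At 30% or more both go.

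On a 900 ms rhythm, the pair 675, 1125 ms (25% early) loses only the 1125. A lone 675 loses nothing.

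**Size in one record, by formula.** A 10-minute record at an assumed 900 ms has 600/0.9 = 667 intervals. Raising rMSSD from 32.76 to 45.98 needs 45.98² − 32.76² = 2114.2 − 1073.2 = 1041 ms² more mean squared difference. A retained early beat adds 6(e × 900)²/667 if its pause is kept (the differences are −e, +2e, −e) and 2(e × 900)²/667 if the pause is deleted.
- 15% early: 6 × 135²/667 = 164; 1041/164 ≈ 6.3 beats.
- 20% early: 6 × 180²/667 = 291; 1041/291 ≈ 3.6 beats.
- 25% early: 2 × 225²/667 = 152; 1041/152 ≈ 6.9 beats.

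**Size in one record, by simulation.** First-order autoregressive series, 667 intervals, mean 900 ms, SDNN 50.98 and rMSSD 32.76 (Table 3 baseline), with five early beats and full pauses. The uncontaminated rMSSD is about 32.7 ms.

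| Prematurity | rMSSD, raw window (ms) | rMSSD, cleaned window (ms) |
|---|---|---|
| 15% | about 43 | about 43 |
| 20% | about 48 | about 48 |
| 25% | about 46 | about 46 |
| 30% | about 40 | about 44 |
| 35% | about 34 to 35 | about 37 to 38 |

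Background variability blurs the sharp cut-offs above, which is why the simulation differs a little from the formula. SDNN rises about 5 to 8% at 15 to 25% prematurity. If differences across deleted intervals are skipped, rMSSD at 15 to 25% is still about 42 to 47 ms. Excluding both intervals of each early beat, with no differences across gaps, returns it to 32.6-32.9 ms.

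**Normal intervals lost.** None in the isolated-beat simulations. After a double detection (180, 720 ms) the raw-window reading deletes the 180 and three normal intervals. After a 2700 ms gap it deletes the 2700 and four normal intervals. With a cleaned window, only the 180 or the 2700 goes.

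**Size in the trial.** One participant raised by 13.22 ms moves an arm mean of 10 by 13.22/10 ≈ 1.3 ms. The pilot SD of change is 3.00 × √18 = 12.7 ms, so the 95% half-width at 10 per arm is 2.101 × 12.7 × √(2/10) ≈ 12.0 ms. If 10 to 30% of recordings carry one to five such beats (assumed), the variance of change rises about 9 to 21%: 12.0 × √1.09 ≈ 12.5 and 12.0 × √1.21 ≈ 13.2 ms.

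**The case against.** The strongest reply is that the rule may not touch the analysed data. The Nevrokard pipeline has its own SDNN and rMSSD, and the protocol does not say that the Matlab values are the ones used. That stands, and it is why the first repair is to name the pipeline. It does not clear the plan, because the Nevrokard description states no rule for editing beats.

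A second reply is that the custom software draws on published archive code, which may treat gaps sensibly. It may, but skipping the gaps still leaves a clear inflation, because the early beats themselves are retained.

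Third, the documents give no ectopy frequency, prematurity, pause type or mean interval. The trial-level figure is therefore conditional. The pilot SD may already contain such noise, so adding it again may count it twice. With no ectopy or artefact the effect is nil. The return to 32.6-32.9 ms assumes that every ectopic pair is identified. All of this stands.

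A reader might infer more than the documents support:
- **That the rule generally keeps premature beats and deletes normal ones.** With a raw window, most beats 35% or more early are removed. What is deleted after an isolated early beat is its pause, which is not a normal-to-normal interval. Normal intervals are lost only after double detections, long gaps or runs, and only if the window uses raw samples, which the text leaves open.
- **That double detections inflate rMSSD just as much.** Five of the 180, 720 ms pattern give about 39.5 ms, not 46.
- **That the rule favours HIRREM.** An early beat at V1 lowers the change score as surely as one at V3 raises it, and nothing in the documents makes ectopy differ by arm.

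**Conclusion.** The concern holds in a limited form. As written, the rule cannot deliver the normal-to-normal series that the protocol requires, because isolated beats less than about 30% early pass through it. A handful can shift one record's rMSSD by as much as the pilot group change, under either reading of the window. That compares one person's record with a group mean. It does not show that the pilot result was artefact or that the trial result would be.

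For the trial, expect extra variance in secondary HRV outcomes: a half-width about 4 to 10% wider (12.5/12.0 to 13.2/12.0) under the assumed 10 to 30% of affected recordings. The primary outcome comes from a seated oscillometric device and is unaffected. The result rests on the assumed 900 ms mean interval, full pauses and the stated prematurity. The change is worth making because the stated rule is poor and a better one is cheap.

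**What to change.** - State which pipeline, Nevrokard or Matlab, supplies the analysed HRV values.
- Replace the 30% rule with labelling of normal beats on the ECG already recorded. Exclude both intervals belonging to any non-normal or mis-detected beat.
- Compute SDNN on the remaining normal-to-normal intervals, and rMSSD only from differences between two adjacent normal intervals, never across a gap. For spectral measures, interpolate over excluded intervals.
- If an automatic screen is kept, compare each interval with a local median of accepted intervals on both sides. Tightening the threshold alone is not enough: at 20%, four early beats with full pauses still leave rMSSD 5.4, 2.8 and 0.8 ms too high at 15, 20 and 25% prematurity.
- Report the percentage of intervals excluded, per recording and by arm.

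The cost is one paragraph of protocol text, a change to the script, analyst time to check beat labels, and slightly fewer usable intervals in some recordings. No new data are needed.
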